2.2.1. Primary Estimand

There are two intercurrent events considered for Part 1 DB phase of this study, (1) the initiation of prohibited medications, and (2) the discontinuation of the study treatment (etrasimod or placebo) due to any reason. Estimand E1 is an estimand strategy for a binary endpoint at a visit, when applied to the primary endpoint of IGA response at Week 16, it is known as the primary estimand. Estimand E1 is illustrated using the primary endpoint below.

Estimand E1 for a binary endpoint at a visit:

Estimand E1 uses a composite strategy and estimates the treatment effect at a visit considering a participant as non-responder after experiencing the intercurrent event of initiation of prohibited medications or discontinuation of study treatment. The primary estimand is Estimand E1 applied to the primary endpoint of IGA response at Week 16, and is defined according to the primary objective. The primary estimand is defined by the following five attributes:

- 1. Treatment condition: received study intervention of etrasimod 2 mg QD or placebo.
- 2. Population: Participants with moderate-to-severe AD as defined by the inclusion and exclusion criteria.
- 3. Variable: IGA response at Week 16 is score of clear (0) or almost clear (1) and a reduction from baseline of ≥2 points. A participant who experiences the intercurrent event of initiation of prohibited medications or discontinuation of study treatment due to any reason (whichever is earlier), will be considered an IGA non-responder (ie, treatment failure) at Week 16.

4. Intercurrent events:

- Initiation of prohibited medications a participant who receives prohibited medications post-randomization prior to the Week 16 visit will be considered an IGA non-responder (ie, treatment failure) at Week 16.
- Discontinuation of study intervention due to any reason prior to the Week 16 visit

 a participant who discontinues study treatment due to any reason will be
 considered an IGA non-responder (ie, treatment failure) at Week 16.
- 5. Population-level summary: The difference in IGA response rates at Week 16 between etrasimod 2 mg QD and placebo.

2.2.2. Secondary Estimands

Estimand E1 will be similarly applied to the binary secondary endpoint (ie, EASI-75 at Week 16) as well as the binary exploratory endpoints (eg, ≥4-point reduction from baseline in PP-NRS score at Week 16) with the endpoint substituted appropriately.

Estimand E2 strategy is defined for a continuous secondary endpoint at a visit (eg, percent change from baseline in EASI score at Week 16).

Estimand E2 for a continuous endpoint at a visit:

Estimand E2 uses a composite strategy and estimates the treatment effect at a visit considering a participant as having no treatment benefit after experiencing the intercurrent event of initiation of prohibited medications or discontinuation of study treatment. Estimand E2 is applied to the secondary endpoint of percent change from baseline in EASI score at Week 16, and is defined according to the secondary objective. This Estimand E2 is defined by the following five attributes:

- 1. Treatment condition: received study intervention of etrasimod 2 mg QD or placebo.
- 2. Population: Participants with moderate-to-severe AD as defined by the inclusion and exclusion criteria.
- 3. Variable: Percent change from baseline in EASI score at Week 16. If a participant in the etrasimod 2 mg QD group experiences the intercurrent events of initiation of prohibited medications or discontinuation of study treatment due to any reason (whichever is earlier), the endpoint data after the intercurrent event (Appendix 3, Post-intercurrent-event data) will be treated as missing and then imputed via multiple imputations as if they are in placebo group (ie, no treatment benefit).

4. Intercurrent events:

- Initiation of prohibited medications a participant who receives prohibited medications post-randomization prior to Week 16, the endpoint data after the intercurrent event (Appendix 3, Post-intercurrent-event data) will be treated as missing and then imputed via multiple imputation as if they are in placebo group (ie, no treatment benefit).
- Discontinuation of study intervention due to any reason prior to the Week 16 visit a participant who discontinues study treatment due to any reason, the endpoint data after the intercurrent event (Appendix 3, Post-intercurrent-event data) will be treated as missing and then imputed via multiple imputation as if they are in placebo group (ie, no treatment benefit).
- 5. Population-level summary: The mean difference in percent change from baseline in EASI score at Week 16 between etrasimod 2 mg QD and placebo.

Estimand E2 will also be applied to percent change from baseline in EASI score at visits prior to Week 16.

2.2.3. Additional Estimand

One supportive estimand is defined to support the Estimand E1 (primary estimand) of the primary endpoint (IGA response at Week 16) as well as Estimand E1 of IGA response at all visits prior to Week 16. It is Estimand E1a, detailed below.

Estimand E1a for IGA response at Week 16:

Estimand E1a uses a treatment policy strategy and estimates the treatment effect at a visit regardless of initiation of prohibited medications or discontinuation of study treatment. This supportive estimand is defined by the following five attributes:

- 1. Treatment condition: received study intervention of etrasimod 2 mg QD or placebo.
- 2. Population: Participants with moderate-to-severe AD as defined by the inclusion and exclusion criteria.
- 3. Variable: IGA response at Week 16 is score of clear (0) or almost clear (1) and a reduction from baseline of ≥2 points. The intercurrent events of initiation of prohibited medications or discontinuation of study treatment due to any reason will not be considered here. All IGA data collected including those collected after the intercurrent events are also included to derive the IGA response at Week 16.

4. Intercurrent events:

- Initiation of prohibited medications is not considered for data exclusion.
- Discontinuation of study intervention due to any reason is not considered for data exclusion.
- 5. Population-level summary: The difference in IGA response rates at Week 16 between etrasimod 2 mg QD and placebo.

The difference between Estimand E1 and E1a is that Estimand E1a disregards intercurrent events and includes all data collected regardless of intercurrent events.

One supportive estimand is defined to support the Estimand E2 of the continuous secondary endpoint at a visit (eg, percent change from baseline in EASI score at Week 16). It is Estimand E2a, detailed below.

Estimand E2a for percent change from baseline in EASI score at Week 16:

Estimand E2a uses a treatment policy strategy and estimates the treatment effect at a visit regardless of initiation of prohibited medications or discontinuation of study treatment. Estimand E2a is applied to the secondary endpoint of percent change from baseline in EASI score at Week 16. This Estimand E2a is defined by the following five attributes:

- 1. Treatment condition: received study intervention of etrasimod 2 mg QD or placebo.
- 2. Population: Participants with moderate-to-severe AD as defined by the inclusion and exclusion criteria.
- 3. Variable: Percent change from baseline in EASI score at Week 16. The intercurrent events of initiation of prohibited medications or discontinuation of study treatment will not be considered here. All data collected including those collected after the intercurrent events are also included in statistical analysis at Week 16.

4. Intercurrent events:

- Initiation of prohibited medications is not considered for data exclusion.
- Discontinuation of study intervention due to any reasons is not considered for data exclusion.
- 5. Population-level summary: The mean difference in percent change from baseline in EASI score at Week 16 between etrasimod 2 mg QD and placebo.

Estimand E2a will also be applied to percent change from baseline in EASI score at visits prior to Week 16.

It can be noted that Estimand E1a for binary efficacy endpoint and Estimand E2a for continuous efficacy endpoint use the same treatment-policy strategy in estimand definition. No estimands will be defined for efficacy endpoints in Part 1 OLE and Part 2 OL Safety phases, and all safety endpoints in this study, so all data collected in these phases will be used in analyses.

2.3. Study Design

This is a 2-part study with Part 1 being 16-week, randomized, DB, placebo controlled, with an OLE, to assess efficacy and safety of 2 mg etrasimod administered orally, QD in participants with refractory, moderate-to-severe AD, whose disease is not adequately controlled with other systemic drug products, including biologics, or when use of those therapies is inadvisable (ie, participants with a history of a prior systemic treatment failure). The OL Part 2 is to assess long-term safety of etrasimod 2 mg QD in participants with moderate-to-severe AD with a history of prior systemic therapy failure.

Part 1: Approximately 60 participants with moderate-to-severe AD with a history of prior systemic treatment failure will be randomized (1:1 ratio) in a double-blind manner to receive etrasimod 2 mg QD or placebo orally, once daily, for 16 weeks. Randomization will be stratified by disease severity as measured by IGA score (3 [moderate AD], 4 [severe AD]) at baseline. Following completion of the double-blind, placebo-controlled period, all participants with no clinically significant treatment-related safety concerns will be given the option to continue in an OLE whereby they will receive etrasimod 2 mg (tablet) QD for 52 weeks. Non-responders, participants not achieving EASI-50, will be discontinued at Week 32 (ie, 16 weeks of treatment in the OLE period).

Part 2: An interim analysis will be conducted after all applicable Part 1 participants have completed the 16-week DB treatment period. The IA will be performed by the Sponsor and data summaries will be shared with the study team. The study team will review the data in the context of the overall benefit-risk profile of etrasimod for the treatment of moderate-to-severe AD with prior systemic failure. The data review will include but is not limited to, efficacy measures of IGA and EASI-75 response and safety parameters including the incidence and severity of AEs, AESIs, and clinically relevant changes in ECG, and vital signs, and laboratory values. The efficacy and safety data will be utilized to make a go/no-go decision for initiating Part 2 of the study, as well as for completing the 52-week treatment for the Part 1 participants in the OLE. Once the decision is made it will be promptly communicated to the sites.

[figure not shown]
If the IA results in a decision to proceed to Part 2 of the study, approximately 340 additional (de novo) participants will be enrolled to receive etrasimod 2 mg orally, once daily, for 52 weeks in an open-label manner in order to fulfill the safety database requirements. Enrollment into Part 2 will not begin until the IA data from Part 1 DB are reviewed, and determination made as to the favorable benefit/risk of etrasimod 2 mg QD in this new target

population. Non-responders, ie, participants not achieving at least EASI-50 will be discontinued at Week 16, Part 2. The participant population in both Part 1 and Part 2 will include at least 40% of participants with moderate AD (IGA score of 3) and at least 40% of participants with severe AD (IGA score of 4). Figure 1 below provides a schematic of this study design.

The application of topical emollients/moisturizers (including those containing ceramide, hyaluronic acid, or urea) will be required at least once daily for at least 1 week prior to baseline (Day 1) and throughout the treatment period without change (ie, type, frequency, application). TCS and other medicated topical treatments for AD must be discontinued at least 1 week prior to baseline (Day 1) and are not permitted in the double-blind treatment period. Safety follow-up visits will occur at 2 and 4 weeks after the last dose of study treatment. Medicated and non-medicated rescue medications are not permitted during the Part 1 DB portion. For Part 1 OLE and Part 2 medicated and non-medicated topical treatments for AD will be permitted at the discretion of the investigator and in accordance with their usual practice.

Figure 1. Study Schematic

PART 1 (N=60) DOUBLE-BLIND EFFICACY AND SAFETY STUDY WITH A 52-WEEK OPEN-LABEL EXTENSION

3. ENDPOINTS AND BASELINE VARIABLES: DEFINITIONS AND CONVENTIONS

3.1. Primary Endpoints

For Part 1 DB,

• IGA response at Week 16.

IGA response is defined as clear (0) or almost clear (1) on a 5-point scale and a reduction of ≥ 2 points from baseline (Appendix 2.2.1). Only participants with baseline IGA ≥ 2 in the FAS are included in all analyses of IGA response.

For Part 1 OLE and Part 2,

- Incidence and severity of treatment-emergent AEs, AEs leading to study treatment discontinuation, SAEs, and AESIs.
- Incidence of clinically significant changes in clinical laboratory values, ECG measurements and vital signs.

3.2. Secondary Endpoints

For Part 1 DB,

• EASI-75 at Week 16.

EASI-75 response is defined as \geq 75% reduction in EASI from baseline (Appendix 2.2.3).

• Percent change from baseline in EASI score at Week 16 (Appendix 2.2.3).

3.3. Exploratory Endpoints

For Part 1 DB,

- IGA response at at all timepoints except Week 16.
- EASI-75 at all timepoints except Week 16.
- Percent change from baseline in EASI score at all timepoints except Week 16.
- ≥4-point reduction in PP-NRS score from baseline at all timepoints (Appendix 2.2.4). Only participants with baseline PP-NRS ≥4 in the FAS are included in all analyses of this endpoint.
- ≥4-point reduction in Skin Pain NRS score from baseline at all timepoints
 (Appendix 2.2.5). Only participants with baseline Skin Pain NRS ≥4 in the FAS are
 included in all analyses of this endpoint.

• EASI-90 at all timepoints.

EASI-90 response is defined as \geq 90% reduction in EASI from baseline (Appendix 2.2.3).

• ≥4-point reduction in POEM from baseline at Week 16 (Appendix 2.2.6). Only participants with baseline POEM ≥4 in the FAS are included in all analyses of this endpoint.

For Part 1 OLE and Part 2,

- EASI-75 at all scheduled timepoints.
- IGA of clear (0) or almost clear (1) on a 5-point scale at all scheduled timepoints.

It is important to note that this is different from IGA response, in that this is without the >2-point reduction component.

- Percent change from baseline in EASI score at all scheduled timepoints.
- ≥4-point reduction in PP-NRS score from baseline at all scheduled timepoints. Only participants with baseline PP-NRS ≥4 are included in all analyses of this endpoint.
- ≥4-point reduction in Skin Pain NRS score from baseline at all scheduled timepoints. Only participants with baseline Skin Pain NRS ≥4 are included in all analyses of this endpoint.
- EASI-90 at all scheduled timepoints.
- Change from baseline in POEM at all scheduled timepoints.

3.4. Baseline Variables

For Part 1 DB and OLE, baseline value for efficacy and safety endpoints is defined as predose value obtained on Day 1 (ie, baseline visit) or prior (if the Day 1 value is not available) in the Part 1 double-blind phase in the analyses. For Part 2, baseline value is defined as predose value obtained on Day 1 (ie, baseline visit) or prior (if the Day 1 value is not available) in the Part 2 open-label phase in the analyses.

A participant's baseline IGA score value (3 [moderate AD], 4 [severe AD]) recorded in the clinical database will be used as the actual IGA stratification factor for both Part 1 and Part 2. If a participant is randomized but the actual baseline IGA is less than 3 (ie, protocol deviation), this participant will be grouped in the actual stratum of baseline IGA score of 3, in order to keep the participant in analyses. This is described in more detail below.

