6.5. Study Intervention Compliance

When participants self-administer study intervention(s) at home, compliance with study intervention will be assessed at each visit through a combination of the accounting of unused study intervention returned by the participant at the study visits and discussion (direct questioning) with the participant which will be documented in the source documents and CRF. Deviation(s) from the prescribed dosage regimen should be recorded in the CRF.

A record of the number of tablets dispensed to and taken by each participant must be maintained and reconciled with study intervention and compliance records. Intervention start and stop dates, including dates for intervention delays, will also be recorded in the CRF.

Part 1: The Week 16 visit is the first dose of open label (etrasimod) treatment. Sites must contact participants 1-2 business days prior to the Week 16 visit to remind them not to take study intervention on the day of the Week 16 visit. Should the participant come to the site having already taken study intervention, all Week 16 procedures will be completed, except for administering open label treatment and first-dose cardiac monitoring procedures for which an unplanned visit is required as soon as possible (within 3 days). The unplanned visit should be scheduled in the morning and not on a Friday or day before a site-observed holiday. The participant will continue taking blinded study intervention up to 1 day prior to the unplanned visit. Again, sites must contact the participants 1-2 business days prior to the unplanned visit to remind them not to take study intervention the day of the visit. The unplanned visit will be the start of the OLE period. See Section 10.10.3 for details of first-dose cardiac monitoring procedures.

The following non-compliance cases will be considered **medication errors** and will be discussed with the sponsor for possible withdrawal from the study:

- 1. Participants interrupting study intervention for ≥ 2 consecutive days within the first week of treatment or Week 16 of Part 1, or for ≥ 7 consecutive days after the first week of treatment (excluding Week 16 of Part 1 where missing 2 doses applies).
 - NOTE The first-dose cardiac monitoring outlined in Section 10.10.3 must be performed any time a participant reinitiates study treatment following dose interruptions as described above and the participant must take the next dose of study treatment at the study site.

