9.5. Sample Size Determination

Part 1: Approximately 60 participants will be randomized to etrasimod 2 mg QD or placebo in a ratio of 1:1 (30 participants per treatment group). This is an estimation study. The primary objective will be to estimate the proportion (95% CI) of participants achieving IGA response at Week 16 in each treatment group and the difference (95% CI) in proportions between the two groups.

With 30 participants per group, assuming the proportions of participants achieving IGA response at Week 16 are 9% and 39% for placebo and etrasimod 2 mg QD, respectively:

- the half-width of the 2-sided 95% CI for the proportion of participants achieving IGA response at Week 16 will be ≤ 17.5% in each treatment group using normal approximation.
- the half-width of the 2-sided 95% CI for the difference in proportions between etrasimod 2 mg QD and placebo will be 20.2% using normal approximation.

The placebo response rate was estimated based on Phase 3 studies in literature. 42-44

No adjustment for multiplicity will be made.

Part 2: Approximately 340 participants are planned in order to fulfill the safety database requirements. No formal sample size calculations are performed.

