2.2. Study Objectives, Endpoints, and Estimand

Table 3. Objectives, Endpoints, and Estimands

Type	Objective	Endpoint	Estimand
Primary			
Efficacy	Part 1 DB: To evaluate the efficacy of etrasimod 2 mg QD versus placebo in adult participants with moderate-to-severe AD and a history of a prior systemic therapy failure.	• Proportion of participants achieving IGA of clear (0) or almost clear (1) (on a 5-point scale) and a reduction of ≥2 points from baseline at Week 16.	• Estimand E1 (Primary Estimand): The difference in the proportions of the binary endpoint between etrasimod 2 mg QD and placebo in patients with moderate-to-severe AD and a history of a prior systemic therapy failure. More details of Estimand E1 (Primary Estimand) are described in Section 2.2.1.
Safety (depending on Part 1 DB IA results)	Part 1 OLE and Part 2 OL Safety: To evaluate the long-term safety of oral etrasimod 2 mg QD in adult participants with moderate-to-severe AD and a history of a prior systemic therapy failure.	 Incidence and severity of treatment-emergent AEs, AEs leading to study treatment discontinuation, SAEs, and AESIs. Incidence of clinically significant changes in clinical laboratory values, 	Not applicable.

Table 3. Objectives, Endpoints, and Estimands

Type	Objective	Endpoint	Estimand
		ECG measurements and vital signs.	
		Note: Baseline for Part 1 is the pre-dose Day 1 in Part 1. Baseline for Part 2 is the pre- dose Day 1 in the Part 2 OL Safety phase.	
Secondary	D +1DD 77		
Efficacy	Part 1 DB: To evaluate the efficacy of etrasimod 2 mg QD versus placebo in adult participants with moderate-to-severe AD and a history of a prior systemic therapy failure.	Proportion of participants achieving EASI-75 at Week 16.	Estimand E1: described above. More details of Estimand E1 are described in Section 2.2.2.
		Percent change from baseline in EASI score at Week 16.	Estimand E2: The mean difference in percent change from baseline in EASI score between etrasimod 2 mg QD and placebo in patients with moderate-to-severe AD and a history of a prior systemic therapy failure. More details are described in Section 2.2.2.
Exploratory	 		

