6.4.3. Study Treatment Duration

Within any study phases (Part 1 DB, Part 1 DB+OLE, or Part 2 OL Safety), study treatment duration (in day) is defined as the time from the day of first dose (ie, Day 1) to the day of last dose of the study treatment. Besides descriptive summaries of the study treatment duration, the number of participants (%) will also be summarized by the following categories (where the upper limits correspond to the target day of the visit windows, Appendix 2.1), and ≥ categories, which are aligned with the protocol's study visits.

 Table 5.
 Reporting Categories for Study Treatment Duration (in Day)

Part 1 DB		Part 1 DB + OLE		Part 2 OL Safety	
Categories	≥ Categories	Categories	≥ Categories	Categories	≥ Categories
(day)	(day)	(day)	(day)	(day)	(day)
1	≥ 1	1	≥ 1	1	≥ 1
2 - 29	≥ 2	2 – 29	≥ 2	2 - 29	≥ 2
30 - 57	≥ 30	30 - 57	≥ 30	30 - 57	≥ 30
58 – 85	≥ 58	58 - 85	≥ 58	58 – 113	≥ 58
86 - 113	≥ 86	86 – 113	≥ 86	114 – 169	≥ 114
≥ 114	≥ 114	114 – 141	≥ 114	170 - 253	≥ 170
		142 – 169	≥ 142	254 - 309	≥ 254
		170 - 225	≥ 170	310 – 365	≥ 310
		226 – 281	≥ 226	≥ 366	≥ 366
		282 - 365	≥ 282		

DMB02-GSOP-RF02 7.0 Statistical Analysis Plan Template 31-Jan-2022

Part	Part 1 DB		Part 1 DB + OLE		Part 2 OL Safety	
Categories	≥ Categories	Categories	≥ Categories	Categories	≥ Categories	
(day)	(day)	(day)	(day)	(day)	(day)	
		366 – 477 > 478	≥ 366 > 478			

Table 5. Reporting Categories for Study Treatment Duration (in Day)

The upper limit of period category corresponds to visit window's target day (target week x 7 days + 1 day).

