6.5.4. Electrocardiograms

Changes from baseline for the ECG parameters QT interval, heart rate, QTc interval, PR interval, and QRS complex will be summarized by treatment and time.

Changes from baseline for the ECG parameters HR, QTcF, PR interval, and QRS complex will be summarized by treatment and time. The frequency of uncorrected QT values above 500 ms will be tabulated.

The number (%) of participants with maximum post-dose QTcF values and maximum increases from baseline in the following categories will be tabulated by treatment.

 Table 6.
 Safety QTcF Assessment

Degree of Prolongation	Mild (ms)	Moderate (ms)	Severe (ms)
Absolute value	>450 – 480	>480 - 500	>500
Increase from baseline		30-60	>60

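### The SAP defines no pre-etrasimod baseline for participants who switch from placebo, so their open-label safety changes mix placebo-period and etrasimod-period change

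*SAP*

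**What the plan says.** SAP 3.4 fixes the reference point for both phases of Part 1: "For Part 1 DB and OLE, baseline value for efficacy and safety endpoints is defined as predose value obtained on Day 1", or an earlier value if Day 1 is missing. The note to the open-label safety objective in SAP Table 3 (section 2.2) repeats it: "Baseline for Part 1 is the pre-dose Day 1 in Part 1". That objective has as a primary endpoint "Incidence of clinically significant changes in clinical laboratory values", ECG measurements and vital signs. SAP 3.5.1 adds change from baseline in laboratory values, ECG and vital signs to the safety endpoints it calls primary for the extension.

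For the placebo arm, etrasimod starts later. Protocol 6.5 states: "The Week 16 visit is the first dose of open label (etrasimod) treatment". SAP 5.2 gives these participants their own label from Week 20 onward, Placebo → Etrasimod 2 mg QD.

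Three further rules bear on the point:

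- SAP 6.5.4 says that "participants with maximum post-dose QTcF values and maximum increases from baseline in the following categories will be tabulated by treatment".
- Study treatment duration in SAP 6.4.3 "is defined as the time from the day of first dose (ie, Day 1) to the day of last dose of the study treatment".
- SAP Appendix 2.1 (Table 8, note b) assigns everything except adverse events collected on the switch day to Week 16 or earlier. When two observations in a window are equally close to the target day, the later one is used.

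**The concern.** The extension's primary aim is the long-term safety of etrasimod. For someone who took placebo for 16 weeks, the state before etrasimod is the Week 16 predose assessment, not Day 1. With Day 1 as the only reference, whatever changed on placebo stays inside every later change from baseline in that group. At stake is whether the extension can show a change on etrasimod for the switched participants: individual shifts, the spread of change, and the QTcF-increase categories.

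The data needed are already scheduled. The Schedule of Activities (Protocol 1.3.1) has vital signs and ECG before dosing at Week 16, with haematology, chemistry and TBNK counts at the same visit. Haematology and TBNK samples must be drawn before dosing. Protocol 10.10.3 applies the Day 1 monitoring procedures, with their predose comparison, to the Week 16 visit. Site monitoring therefore appears to use a same-visit reference that the SAP's summaries lack.

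**Working it through.** **Inputs.** Target-day rule, "target week x 7 days + 1 day" (SAP 6.4.3, Table 5 footnote). Week 16 visit window ±5 days (Protocol 1.3.1), plus up to 3 days if the switch moves to an unplanned visit (Protocol 6.5). About 30 participants per arm (Protocol 9.5); the number entering the extension is not stated.

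**1. The plan's own day.** 16 × 7 + 1 = 113, as in SAP Table 8. Baseline to first etrasimod dose for a switcher is 113 − 1 = 112 days, or 16 weeks. With the visit window it is 107 to 117 days; with the unplanned visit it is up to 118 + 3 − 1 = 120 days.

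**2. What a change from Day 1 contains.** Write Y0 for Day 1, Y16 for Week 16 predose and Yt for a later visit. Then

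Yt − Y0 = (Y16 − Y0) + (Yt − Y16).

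The first bracket is placebo-period change and the second is change on etrasimod. In the mean, the excess over the etrasimod-period change is exactly the mean placebo-period change.

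**3. Share of the interval spent on placebo,** 112 / (7 × week):

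| Visit | Days since Day 1 | Days since switch | Placebo share |
|---|---|---|---|
| Week 20 | 140 | 28 | 80% |
| Week 24 | 168 | 56 | 67% |
| Week 32 | 224 | 112 | 50% |
| Week 40 | 280 | 168 | 40% |
| Week 52 | 364 | 252 | 31% |
| Week 68 | 476 | 364 | 24% |

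These are shares of time, not of effect.

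**4. Maximum QTcF increase.** After the first dose of study treatment, a switcher who completes has four scheduled ECGs: Day 1 Hour 4, Week 16 predose, Week 16 Hour 4 and Week 68. The first two are on placebo. SAP 6.5.4 does not say over which period the maximum is taken. Over the double-blind and open-label phases together, it can come from a placebo visit. Over open-label visits alone, the switch-day readings drop out under note b and only Week 68 remains, still measured against Day 1.

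**5. Switch-day readings.** The Week 16 predose and Hour 4 ECGs fall on the same day and so tie for distance from the target day. Read literally, the later one is used, it is assigned to Week 16, and visits up to Week 16 carry the label Placebo (SAP 5.2). A value taken after the first etrasimod dose could then be reported as placebo data. Appendix 2.1 suggests post-dose ECG labels for Day 1 only.

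**6. Treatment duration.** A switcher who stops on Day 365 is shown with 365 days; the etrasimod days are 365 − 113 + 1 = 253. At Day 477, 112 of 477 days (23.5%) are placebo and 365 are etrasimod.

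**7. After the change.** For tests with a Week 16 predose value, the reference moves from 112 days before the first etrasimod dose to the same visit. The Week 68 change then spans 364 days, all on etrasimod, instead of 476.

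**The case against.** A reader might infer that placebo-period changes are counted as etrasimod changes. The documents do not support that. Switchers are not merged with the etrasimod arm, their column names the switch, and the by-visit tables in SAP 6.5.2 to 6.5.4 show their change up to Week 16. Mean drift is therefore partly visible. But subtracting the Week 16 mean from a later mean gives no standard deviation, no participant-level shift and no QTcF-increase category. The denominators also differ when participants do not enter the extension, and for ECG and vital signs the Week 16 value may itself be post-dose.

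A reader might also infer that all open-label safety results are affected. They are not. Treatment-emergent adverse events are defined by onset date (SAP 3.5). Laboratory high/low categories, absolute QTcF categories and QT above 500 ms use no baseline value. The cumulative double-blind plus open-label adverse event display does span the placebo period, but that concerns the display period, not the baseline.

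Nor do the eligibility limits at entry make the switched column alone drift towards abnormal. Regression to the mean after those limits acts on both arms, and moving one arm's baseline would remove it from one column only.

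The duration rule is not an error as labelled. It reports study treatment, which Protocol 6 defines as etrasimod and placebo, and the double-blind duration is tabulated separately. Etrasimod exposure would be an added row.

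Finally, all safety analyses are descriptive, and Part 2, with about 340 planned participants, has a baseline before etrasimod. This limits the weight of the point but does not remove it.

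**Conclusion.** The point holds in a limited form. In at most about 30 participants, open-label changes from baseline in laboratory values, vital signs and ECG, including the maximum QTcF increase, combine about 112 days of placebo-period change with change on etrasimod, and the planned tables do not allow the two to be separated at participant level. Day 1 is the right reference for the double-blind analyses, for participants randomized to etrasimod and for open-label efficacy.

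Neither the size nor the direction of the distortion can be derived: the documents give no placebo-period safety changes, standard deviations or correlations. The day counts assume visits on schedule. The reading of switch-day data rests on applying the Appendix 2.1 rules literally; the programming plan may intend something else, but the SAP does not say so. This is worth correcting because it touches a primary open-label safety summary and is cheap. It does not threaten the trial's efficacy conclusions.

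**What to change.** - **SAP 3.4 and 6.5.2 to 6.5.4:** for the Placebo → Etrasimod group's open-label safety change, shift and QTcF-increase tables, add a baseline equal to the last non-missing value before the first etrasimod dose. This is Week 16 predose where collected. Urinalysis and coagulation have no scheduled Week 16 sample, so they stay on Day 1 with a footnote.
- **SAP 6.5.4:** in that table, take the maximum QTcF increase only over values after the first etrasimod dose.
- **SAP Appendix 2.1:** label Week 16 predose and post-dose vital signs and ECG separately, so that readings after the first open-label dose are not reported as placebo Week 16 data.
- **SAP 6.4.3:** add etrasimod exposure days, counted from the first etrasimod dose.
- **Unchanged:** the Day 1 baseline for double-blind analyses, the etrasimod arm and open-label efficacy.

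The cost is SAP wording and a few derived variables, with no new assessments. No protocol amendment appears necessary: Protocol section 3 states the Day 1 baseline only under exploratory long-term efficacy, and the reference to the Day 1 ECG in Protocol 8.3.3 concerns adverse event assessment. The downside is two baselines to footnote in the Part 1 safety tables, and different reference points in adjacent columns.
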